### **7.2.2. Examination of Subgroups**

Subgroup analyses may be conducted for selected endpoints. Detailed methodology will be provided in the SAP.

### **7.2.3. Handling of Missing Data**

Handling of missing data will be described in the SAP.

### **7.2.4. Baseline Evaluations**

Demographics and other baseline characteristics, including disease-specific information, will be summarized descriptively by treatment arm and overall for the mITT and Safety Analysis Set.

Baseline value for proteinuria will be calculated as the average of two valid 24-hour urine protein levels before randomization.

### **7.2.5. Efficacy Analyses**

#### **7.2.5.1. Primary Endpoint**

The primary endpoint of the study is the percentage reduction from baseline in 24-hour proteinuria at Week 32. The 24-hour urine protein will be log transformed for analyses. The primary analysis will be performed on the change from baseline in log transformed urine protein using a linear model with log transformed baseline urine protein as covariate and treatment and randomization stratification factor as fixed effect. The least square mean difference and its 90% confidence interval will be estimated and then back transformed to original scale.

A sensitivity analysis using all urine protein assessments including a single 24-hour assessment will be conducted using mixed-effects model repeated measures (MMRM) method.

#### **7.2.5.2. Secondary Efficacy Endpoints**

The secondary efficacy endpoints include percent of patients with partial clinical remission (UP <1.0 g/24-hours), percent of patients with >50% reduction in 24-hour proteinuria, change from baseline in UPCR as measured in 24-hour urine at Week 32, change from baseline in urine protein/creatinine ratio (UPCR) as measured in a spot urine at Week 32 and change from baseline in hematuria at Week 32.

The percentage of patients with partial clinical remission or with >50% reduction in 24-hour proteinuria for each treatment arm and the difference between treatment arms will be presented together with an approximate 90% confidence interval based on Wilson score method.

Change from baseline in urine protein / creatinine ratio (UPCR) will be analyzed similarly to the analysis of the primary variable as appropriate. UPCR will be log transformed first before analysis.

#### **7.2.5.3. Exploratory Endpoints**

Change from baseline in exploratory efficacy variables will be summarized. Percent of patients in full clinical remission and incidence of ADA will be tabulated by treatments. Inferential

statistics for exploratory efficacy variables may be presented as needed. Details will be described in the SAP.

The slope of eGFR for the first 32 weeks will be estimated for each subject with the linear regression method using all assessment data during the period.

Descriptive statistics including the number of patients, mean, median, standard deviation (SD), interquartile range (Q1, Q3), minimum, and maximum values will be presented for continuous variables. Frequencies and percentages will be presented for categorical and ordinal variables.

#### 7.2.6. Pharmacodynamic Analysis

Assessment of the PD effect of the treatment will be performed descriptively, including plotting graphically levels of serum C5 protein and CAP/CCP over time and relative to baseline levels. Inferential statistics maybe generated as deemed necessary.

#### 7.2.7. Pharmacokinetic Analysis

Pharmacokinetic analyses will be conducted using noncompartmental methods. Pharmacokinetic parameters include, but will not be limited to: AUC,  $C_{max}$ ,  $T_{max}$ ,  $t_{1/2}$ , CL/F, V/F, cumulative amount excreted unchanged in urine (Ae), and percent of dose excreted (fe) in the urine of cemdisiran (25-mer) and 23-mer.

Other parameters may be calculated, if deemed necessary. Summary statistics and figures will be presented. Inferential statistics may be generated when deemed necessary.

#### 7.2.8. Safety Analyses

The primary parameter is the frequency of treatment-emergent AEs (hereafter referred to simply as AEs). Safety parameters also include vital signs, ECGs, clinical laboratory assessments, and physical exams. The extent of exposure will be summarized by dose level and overall.

Adverse events will be classified according to the Medical Dictionary for Regulatory Activities (MedDRA) System Organ Class and Preferred Term. Prior and concomitant medications will be classified according to the World Health Organization (WHO) drug dictionary. All SAEs occurring before the first dose of study drug and AEs related to study procedures will be listed. The number and percentage of patients experiencing AEs after the first dose of the study drug or events that worsened in severity after dosing will be summarized. AEs will be presented by maximum severity and relationship to study medication. SAEs and AEs leading to discontinuation of treatment will also be tabulated.

By-subject listings will be provided for deaths, SAEs, and AEs leading to study discontinuation.

Frequency of adverse events of clinical interest will also be summarized and by-subject listings will be provided.

Descriptive statistics will be provided for clinical laboratory data, 12-lead ECG interval data and vital signs data, presented as both actual values and changes from baseline over time. Laboratory shift tables from baseline to worst values will be presented. Baseline will be defined as the last observation on or prior to Study Day 1.

Abnormal physical examination findings and 12-lead ECG data will be presented in a by-patient data listing. Details of any abnormalities will be included in patient listings.

Other safety summaries will be presented as appropriate. Further details will be specified in the SAP.

All safety analyses will be conducted using the Safety Analysis Set.

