### **4.3.1. Discontinuation of Study Drug or Declining Procedural Assessments**

Reasons for discontinuation of study drug include any of the following:

- Significant violation of the protocol
- Adverse event
- Non-adherence to treatment regimen
- Pregnancy
- Lost to follow-up
- Other reason (non-adverse event), including confirmed positive test for ADA to cemdisiran
- Or, study is terminated by the Sponsor

Patients who are pregnant will be discontinued from study drug dosing immediately (see Section 6.7.5.2 for reporting and follow-up of pregnancy). A positive urine pregnancy test should be confirmed by a serum pregnancy test prior to discontinuing study drug.

Patients who discontinue study drug and/or decline procedural assessments should not be automatically removed from study. In general, patients who discontinue study drug dosing for any reason will be encouraged to remain on the study to complete the remaining assessments through the Week 36/EOS or Week 84/OLE EOS visit and safety follow-up so that their experience is captured in the final analyses.

If this occurs, the Investigator is to discuss with the patient the appropriate processes for discontinuation from study drug and must discuss with the patient the options for continuation of the Schedule of Assessments ([Table 2](#)), including different options for follow-up and collection of data (eg, in person, by phone, by mail, through family or friends, or from options not involving patient contact, such as communication with other treating physicians or from review of medical records), including endpoints and adverse events, and must document this decision in the patient's medical records.

If a patient discontinues dosing due to an AE, including SAEs, the event should be followed as described in Section [6.7.6](#). When a patient discontinues study drug dosing, the primary reason must be recorded in the eCRF. Patients who discontinue study drug and remain on study may receive treatment consistent with local standard practice for their disease per Investigator judgement, as applicable.

Patients who discontinue from study drug during the 36-week treatment period (defined as the time the first dose of study drug is administered on Study Day 1 through completion of the Week 36 assessments) will be encouraged to remain on the study and complete assessments through Week 36; they will also be asked to complete safety follow-up visits 13, 26, 39 and 52 weeks thereafter (see [Table 1](#)).

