### 6.7.1. Vital Signs

Vital signs will be measured as specified in the Schedule of Assessments ([Table 1](#) and [Table 2](#)) and include blood pressure, heart rate, body temperature, and respiratory rate. Vital signs will be measured in the seated or supine position, after the patient has rested comfortably for 10 minutes. On Day 1, vital signs will be collected at predose and 4 hours ( $\pm 15$  minutes) postdose. On all other dosing days, vital signs will be collected predose.

Blood pressure should be taken using the same arm throughout the study. Body temperature in degrees Celsius will be obtained via oral or tympanic method. Heart rate will be counted for a full minute and recorded in beats per minute, and respiration rate will be counted for a full minute and recorded in breaths per minute.

Additional vital sign assessments, as medically indicated, may be added at the discretion of the Investigator, or as per DMC advice.

Vital signs results will be recorded in the eCRF.

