#### **6.7.4.      Electrocardiogram**

Twelve-lead ECGs reporting rhythm, ventricular rate, RR interval, PR interval, QRS duration, and QT interval and Fridericia-corrected QT interval will be obtained, as specified in the Schedule of Assessments ([Table 1](#) and [Table 2](#)). Patients should be supine for at least 5 minutes before each ECG is obtained. A single 12-lead ECG will be performed at Screening. At all other time points, 12-lead ECGs will be performed in triplicate, with readings approximately 1 minute apart. 12-lead ECGs will be performed at predose; 60 minutes postdose; and 4 hours postdose in relation to the Day 1 and Week 32 cemdisiran or placebo doses.

When ECG and blood sample collection occur at the same time, ECGs should be performed before blood samples are drawn.

The Investigator or qualified designee will review all ECGs to assess whether the results have changed since the Baseline visit and to determine the clinical significance of the results. These assessments will be recorded on the eCRF. Additional ECGs may be collected at the discretion of the Investigator, or as per DMC advice.

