#### **6.7.5.      Clinical Laboratory Assessments**

The following clinical laboratory tests will be evaluated by a central laboratory. However, to assess patient eligibility at the end of the run-in period, eGFR will also be assessed locally. Specific instructions for transaminase elevations are provided in [Section 5.2.3.1](#). For any other unexplained clinically relevant abnormal laboratory test occurring after study drug administration, the test should be repeated and followed up at the discretion of the Investigator, or as per DMC advice, until it has returned to the normal range or stabilized, and/or a diagnosis is made to adequately explain the abnormality. Additional safety laboratories and assessments as indicated by the clinical situation may be requested. Clinical laboratory assessments are listed in [Table 5](#) and include: hematology, serum chemistry and urinalysis parameters. Parameters will be assessed as specified in the Schedule of Assessments ([Table 1](#) and [Table 2](#)).

While local laboratory results may be used for urgent clinical and dosing decisions, on the day of the clinic visit assessments, all laboratory assessments specified in [Table 5](#) which are performed at the clinic should also be sent in parallel to the central laboratory. In the case of discrepant local and central laboratory results on samples drawn on the same day, central laboratory results will be relied upon for clinical and dosing decisions.

Clinical laboratory assessments may be collected at the clinical study center or at home by a trained healthcare professional. On dosing days blood samples will be collected predose.

For any safety event or laboratory abnormality, additional laboratory assessments, imaging, and consultation may be performed for clinical evaluation and/or in consultation with the Medical Monitor; results may be collected and should be included in the clinical database.

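### The safety baseline in Protocol Section 7.2.8 is set by day rather than by dose, so read literally it takes the 4-hour postdose ECG and vital signs on Day 1 as baseline

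*Protocol*

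**What the plan says.** Section 7.2.8 gives one baseline definition for the safety analyses: "Baseline will be defined as the last observation on or prior to Study Day 1". It closes a paragraph in which laboratory, ECG interval and vital signs data are to be "presented as both actual values and changes from baseline over time". The rule refers to the study day and contains no predose condition.

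Section 4.3.1, in defining the treatment period, fixes what Study Day 1 is: the "first dose of study drug is administered on Study Day 1".

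The assessment sections set the Day 1 timings:

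- Vital signs (Section 6.7.1): "On Day 1, vital signs will be collected at predose and 4 hours" after dosing.
- ECG (Section 6.7.4): "12-lead ECGs will be performed at predose; 60 minutes postdose; and 4 hours postdose in relation to the Day 1 and Week 32" doses. Apart from Screening, "12-lead ECGs will be performed in triplicate, with readings approximately 1 minute apart".
- Blood for laboratory tests (Section 6.7.5): "On dosing days blood samples will be collected predose".

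Section 6.3, headed as the baseline assessments of the treatment period, lists vital signs and ECG among the procedures to be done on Day 1 before study drug is given.

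**The concern.** A baseline should be free of the treatment whose effect it is used to measure. A rule that admits anything recorded on the day of first dose meets this only if nothing is measured after dosing that day. Here, ECGs and vital signs are.

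The Day 1 postdose ECGs and vital signs are the first opportunity to see an acute effect on QTcF, heart rate or blood pressure. A baseline taken from those readings removes the effect from the Day 1 change and carries it, with opposite sign, into the other changes. The conflict with Section 6.3 also means that two programmers working from the same protocol could produce different tables.

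**Working it through.** The plan gives no figure to reproduce. The check applies the Section 7.2.8 rule to the Day 1 schedule and compares it with a rule anchored to the first dose.

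| Domain | Scheduled on Day 1 | Last on or before Day 1 | Last before first dose |
|---|---|---|---|
| Vital signs | predose, 4 h postdose | 4 h postdose | predose |
| ECG | predose, 60 min, 4 h postdose (triplicate each) | 4 h postdose set | predose set |
| Laboratory blood tests | predose | predose | predose |

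The two rules differ for vital signs and ECG, for any patient with complete Day 1 data. They agree for laboratory blood tests. A patient who misses the 4-hour assessment would have the 60-minute ECG or the predose vital signs as baseline, so the literal rule also lets the baseline time point differ between patients.

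For one patient and one parameter, let P be the predose value, H the 60-minute value, A the 4-hour value and T any later value.

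- Day 1, 4 hours: the intended change is A − P. The literal rule gives A − A = 0, whatever the drug did.
- Day 1, 60 minutes (ECG): the intended change is H − P. The literal rule gives H − A, a comparison with a later treated value.
- Any later visit: the intended change is T − P. The literal rule gives T − A = (T − P) − (A − P), the intended change minus the acute 4-hour change.

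The last line also shows what the placebo arm can and cannot repair. The between-arm difference in mean change moves by minus the between-arm difference in mean (A − P). A shift common to both arms, such as one due to time of day, cancels from that difference, although it remains in each arm's own change. A drug effect at 4 hours is present only in the cemdisiran arm and does not cancel.

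Other sections show where the problem stops. Section 7.2.4 defines the proteinuria baseline separately, as the average of two valid 24-hour collections before randomization. Adverse events in Section 7.2.8 are counted from the first dose and use no baseline value. Laboratory changes and shift tables keep a predose baseline.

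**The case against.** The strongest reply is that the protocol, read as a whole, intends a predose baseline. Section 6.3 says as much, Section 7.2 describes its contents as brief summaries to be completed in the SAP, and Section 7.2.8 ends by deferring further detail there. The SAP is not shown and may state the rule correctly.

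Part of this stands. It is good evidence of intent, and it cannot be assumed that the final tables will follow the literal sentence. But the protocol does not leave the baseline open: it states a rule, and the general deferral does not qualify it. Section 6.3 contradicts that rule; it does not amend it.

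It can also be argued that little harm follows. This largely stands. The summaries are descriptive, and adverse event frequency is the primary safety parameter. Actual values are reported beside the changes, so a difference between predose and 4-hour readings would remain visible. Abnormal ECG findings are listed by patient, and the investigator's review of each ECG does not depend on Section 7.2.8.

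Two stronger readings are tempting, and the documents support neither:

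- A reader might infer that the ECG baseline would be a single reading of the triplicate, inflating within-session error variance up to threefold. No section says that readings are analysed singly; Section 6.7.4 says only that they are taken in triplicate.
- A reader might infer that the Day 1 baseline is also wrong for placebo patients who first receive cemdisiran at Week 36. Section 7.2.8 does not say how exposure summaries for those patients are built. A second baseline for the extension is a separate matter, normally left to the SAP.

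**Conclusion.** The point holds as a wording error in Section 7.2.8 and an inconsistency with Section 6.3. Applied literally, the rule gives a postdose baseline for ECG and vital signs in every patient with complete Day 1 data. It forces the Day 1 4-hour change to zero and shifts each other change by the size of the acute change. That size is unknown: the documents give no acute effect on QTcF, heart rate or blood pressure, so the shift could be negligible.

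The conclusion assumes that the definition covers ECG and vital signs as well as laboratory data, as its general wording and its place in the paragraph indicate, and that it is programmed as written. A reader might go further and infer that the trial plans to measure safety from a treated value, or that its safety conclusions are compromised. Section 6.3 speaks against the first, and the unaffected domains and reported actual values speak against the second. The proportionate rating is should-fix.

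**What to change.** Reword the sentence in Section 7.2.8 so that it is anchored to dosing, for example: *baseline is the last non-missing observation before the first dose of study drug*. For ECG, add that this is the predose Day 1 triplicate and state how it is summarised, for example by its mean. Sections 6.3 and 7.2.8 then agree, and the SAP should carry the same definition.

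The cost is one sentence in the protocol and its counterpart in the SAP. The predose vital signs and ECGs are already scheduled, so no visit, procedure or sample size changes. Laboratory baselines stay as they are.

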### **6.3. Baseline Assessments (Treatment Period)**

Prior to dosing on Day 1, patients will be reassessed for eligibility and blood and urine samples for clinical laboratory assessments and exploratory analyses collected, including blood samples for complement activity tests (CAP/CCP), C5 analysis, PK, ADA and CIC.

In addition, prior to administration of study drug, the following assessments will be performed: full physical examination, body weight and height, vital signs, ECG, urine pregnancy test, eGFR assessment, and urinalysis.

Collection of blood and urine samples for PK analysis on Day 1 will be performed as outlined in [Table 3](#).

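### The safety baseline is cut off by calendar day, so as written it selects the 4-hour postdose Day 1 reading for vital signs and ECG

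*Protocol*

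**What the plan says.** **The rule.** Section 7.2.8 (Safety Analyses) states: "Baseline will be defined as the last observation on or prior to Study Day 1". The cut-off is a day. Nothing in the sentence limits it to readings taken before dosing.

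**What it feeds.** The same section calls for descriptive statistics on laboratory data and on "12-lead ECG interval data and vital signs data, presented as both actual values and changes from baseline over time".

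**Day 1 is the dosing day.** Section 4.3.1 dates the start of the treatment period from "the time the first dose of study drug is administered on Study Day 1".

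**What is measured that day.** Section 6.7.1: "On Day 1, vital signs will be collected at predose and 4 hours" (±15 minutes) postdose; on all other dosing days vital signs are predose only. Section 6.7.4: "12-lead ECGs will be performed at predose; 60 minutes postdose; and 4 hours postdose in relation to the Day 1 and Week 32" doses. It adds, after describing a single Screening ECG: "At all other time points, 12-lead ECGs will be performed in triplicate, with readings approximately 1 minute apart".

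**What Section 6.3 treats as baseline.** Under a heading that names baseline assessments, it says that "prior to administration of study drug, the following assessments will be performed", and the list that follows includes vital signs and ECG.

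**The concern.** A programmer who applies the Section 7.2.8 sentence to the Day 1 records will pick the latest one. For vital signs and ECG that record comes after the first dose. The analysis definition therefore does not match the predose baseline set out in Section 6.3.

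The Day 1 postdose readings are the natural place to look for an acute effect of the first injection on blood pressure, heart rate or ECG intervals. If the last of them is itself the baseline, the change-from-baseline table cannot show an effect at that time, and later visits are compared with a reading taken on drug in the cemdisiran arm. Because placebo patients have no drug effect at 4 hours, comparing the arms does not remove the problem.

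**Working it through.** The plan gives no figure to reproduce. The check applies the rule to the schedule and then follows the algebra.

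**Step 1. Which record does the rule select?**

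| Data | Day 1 schedule | Source | Last Day 1 record |
|---|---|---|---|
| Vital signs | predose, 4 h | 6.7.1 | 4 h postdose |
| ECG | predose, 60 min, 4 h | 6.7.4 | 4 h postdose |
| Laboratory blood samples | predose on dosing days | 6.7.5 | predose |

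For vital signs and ECG the selected record is postdose. For scheduled laboratory blood samples it is predose, so those changes and shift tables are not affected.

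**Step 2. What happens to the changes?** For one patient, let x0 be the predose value, x4 the 4-hour value and xv the value at a later visit. Let d = x4 − x0.

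- Day 1, 4 hours. Predose baseline: x4 − x0 = d. Rule as written: x4 − x4 = 0.
- Day 1, predose. Rule as written: x0 − x4 = −d.
- Later visit. Rule as written: xv − x4 = (xv − x0) − (x4 − x0) = (true change) − d.

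The zero at 4 hours holds for every patient whose 4-hour reading is present, whatever the drug does. The shift of −d holds at every later visit.

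**Step 3. What survives the comparison with placebo?** Write d as a drift common to both arms (time of day, repeat measurement) plus a drug effect e, with e = 0 on placebo. The difference between arms in mean change at a later visit is then the true difference minus the mean of e. The common drift cancels; e does not.

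**Step 4. Week 32 ECGs.** Section 6.7.4 repeats the predose, 60-minute and 4-hour sequence around the Week 32 dose. If the same acute effect e recurred and nothing else had changed, the Week 32 4-hour change would be e − e = 0. The within-visit difference in actual values, 4 hours minus predose, would still be e.

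**Step 5. Missing readings.** A patient without the 4-hour reading would fall back to the 60-minute ECG or the predose vital signs, so baselines could differ in kind between patients.

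The documents give no value for d or e, so none of these shifts can be expressed in mmHg, beats per minute or milliseconds.

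**The case against.** The intent is not in real doubt. Section 6.3 places baseline vital signs and ECG before dosing, and Sections 6.7.1 and 6.7.4 label the later readings postdose. Section 7.2 calls its text a summary, Section 7.2.8 defers further detail to the SAP, and record-level derivation of baseline is ordinary SAP content. The affected tables are descriptive, and no test or dosing rule is tied to this baseline. Actual values are reported beside the changes, so a Day 1 shift would still be visible in the data.

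Most of this stands, and it limits the point. It does not remove it, because the protocol does not leave baseline open: it states a rule, and that rule selects the wrong record. Section 7 also says the SAP is to implement the analyses in line with the protocol's main features.

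Three stronger readings are not supported:

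- A reader might infer that an ECG baseline would be one tracing out of three, with a correspondingly larger reading error. The protocol does not say how replicates are combined, and any inflation factor would require independent errors between tracings about a minute apart, for which no variance or correlation is given.
- A reader might infer that an acute effect would reappear with its sign reversed at every later visit. That requires the effect to be present at 4 hours and absent at each later visit. What follows without that assumption is only that it is subtracted.
- A reader might infer that the protocol hides acute effects altogether. It does not, since actual values are tabulated and Week 32 allows a second within-visit ECG comparison.

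**Conclusion.** The rule is wrong as written for vital signs and ECG and should be corrected. It selects the 4-hour postdose Day 1 reading, makes the 4-hour change zero by construction, and subtracts any acute effect at 4 hours from later changes.

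The reach is limited to the change-from-baseline columns for these two kinds of data, in about 30 randomized patients. Scheduled laboratory blood samples are predose (Section 6.7.5), and the proteinuria baseline, the average of two valid collections before randomization, has its own definition (Section 7.2.4), so the primary endpoint is untouched.

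The conclusion rests on the sentence being applied literally and on the Day 1 readings being taken as scheduled. Whether any reported change would be materially distorted depends on whether the drug has an acute effect at 4 hours, which the documents do not quantify.

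**What to change.** Replace the sentence in Section 7.2.8 with: *Baseline is the last non-missing observation before the first dose of study drug.* For ECG, add that the predose Day 1 triplicate is used, and let the SAP state how its three readings are combined. Report the Day 1 60-minute ECG and the 4-hour vital signs and ECG as post-baseline time points.

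The cost is one sentence in the protocol or SAP. No new data are needed, because the predose readings are already scheduled. Scheduled laboratory baselines stay as they are.
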